9.7.1.6.2 SECONDARY EFFICACY ANALYSES

Analyses for Key Secondary Efficacy Endpoints (revised per Amendment 06):

The key secondary analyses will be performed only if the primary analysis is significant. The treatment effect for elenbecestat 50 mg/day versus placebo, for each key secondary efficacy endpoint, will be tested using a sequential testing procedure at a significance level of 2-sided alpha = 0.05, ie, any test will start only if the test with higher hierarchical order is significant.

The change from baseline in ADCOMS at 24 months will be analyzed using the same MMRM model as the primary efficacy analysis to compare elenbecestat 50 mg per day versus placebo on the FAS, using baseline ADCOMS in the model.

The change from baseline in amyloid PET SUVR at 24 months will be analyzed using the same MMRM model as the primary efficacy analysis to compare elenbecestat 50 mg per day versus placebo on the FAS, using baseline amyloid PET SUVR in the model. The same analysis will be performed within study as key secondary efficacy endpoint analyses.

Analyses for Other Secondary Endpoints (revised per Amendment 06)

The change from baseline in CDR-SB and ADCOMS at 24 months will be analyzed using the same MMRM model as the primary analysis for subjects enriched by baseline PET SUVR between e.g. 1.2 and 1.6 on the FAS.

The rate of change over time (mean slope) based on change from baseline in the CDR-SB will be analyzed using linear mixed effects (LME) models for multivariate normal data derived from a random coefficient model (slope analysis), where the mean slope in each group depends on a continuous assessment time. The LME model will include treatment group, baseline CDR-SB, randomization stratification variables, assessment time, baseline CDR-SB-by-assessment time, and treatment group-by-assessment time. ApoE4 status may be included in the model if appropriate.

Time to worsening of CDR scores by 24 months will be analyzed on the FAS using Cox regression model for treatment effect adjusting for randomization stratification factors. *ApoE4* status may be included in the model if appropriate. (revised per Amendment 06) Time to worsening of a CDR score is defined as time from randomization to worsening of the CDR score (ie, the first worsening in 2 consecutive scheduled visits). For subjects whose CDR scores have not worsened by the end of the Treatment Period of the Core Study, the time to worsening of the CDR score will be censored at the date of last CDR assessment for these subjects.

Time to conversion to dementia for subjects who were not clinically staged as dementia at Baseline based on clinical diagnosis will be analyzed on the FAS using Cox regression model for treatment effect adjusting for randomization stratification factors. *ApoE4* status may be included in the model if appropriate. (revised per Amendment 06) Proportion of subjects with

dementia diagnosis at 24 months will be estimated using Kaplan—Meier method based on time to conversion to dementia based on clinical diagnosis. Time to conversion to dementia for subjects who were not clinically staged as dementia at Baseline based on clinical diagnosis is defined as time from randomization to conversion to dementia based on clinical diagnosis. For subjects without clinical dementia by the end of study, the time to conversion to dementia based on clinical diagnosis will be censored at the date of last dementia diagnosis.

The other continuous secondary efficacy endpoints as defined above will be analyzed using the same MMRM model as the primary efficacy analysis to compare elenbecestat 50 mg per day versus placebo on the FAS, using baseline value corresponding to the response variable in the model.

The relationship between clinical changes at 24 months (CDR-SB, ADCOMS, ADAS-cog14, MMSE, and FAQ) and changes in each of the biomarkers (amyloid PET, tau PET, CSF A β (1-42), t-tau, p-tau, vMRI, and fMRI) at 24 months, will be evaluated using an ANCOVA model. (revised per Amendments 01, 04, 05, and 06) Changes in clinical scales at 24 months will be the response variables and either continuous or categorical change of biomarkers will be independent variables. The ANCOVA model will also include baseline value for clinical scale as a covariate, with treatment group and randomization stratification variables, as factors. *ApoE4* status may be included in the model if appropriate. (revised per Amendment 06)

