Additional secondary endpoints of the study will evaluate the effects of elenbecestat compared to placebo on time to disease progression, time to conversion to dementia, the ADAS-cog14 (including a separate endpoint for the immediate recall and delayed recall subtests), MMSE, and FAQ at 24 months. These scales are also widely used and well recognized instruments in AD trials. A novel composite endpoint, ADCOMS ([Wang, et al., 2016](#)), is also included as a secondary endpoint. (revised per Amendments 01 and 06)

Additional important biomarker endpoints will evaluate the AD modifying properties of elenbecestat by assessing several human AD biomarkers. (revised per Amendment 01) Of note, there is no widely recognized consensus over the utilization of a single AD biomarker as a measure of disease modification. Therefore, it is proposed that several biomarkers will be utilized during this study without a specific hierarchical approach.

The proposed exploratory biomarkers for this study are aimed at evaluating the effects of elenbecestat on disease progression and neurodegenerative (NDG) changes correlating these with clinical benefit. An additional analysis will evaluate whether inhibition of amyloid production by elenbecestat has downstream effects on neurodegeneration (as measured by CSF and brain tau levels that are thought to be associated with neurofibrillary pathology), especially in the EAD population. (revised per Amendment 04)

Randomization and stratification will be used in this study to avoid bias in the assignment of subjects to treatment, to increase the likelihood that known and unknown subject attributes

(eg, demographics and baseline characteristics) are balanced across treatment groups, and to ensure the validity of statistical comparisons across treatment groups. Blinding to treatment will be used to reduce potential bias during data collection and evaluation of endpoints.

Rationale for the selection of doses used in the study is provided in [Section 9.4.4](#).

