9.7.1.1.2 SECONDARY ENDPOINTS

The key secondary endpoints of the study are as follows (revised per Amendment 06):

- Change from baseline in ADCOMS at 24 months in the combined studies
- Change from baseline in amyloid PET SUVR at 24 months for brain amyloid levels in the combined studies
- Change from baseline in amyloid PET SUVR at 24 months for brain amyloid levels in the individual studies

The other secondary endpoints of the study are as follows (revised per Amendment 06):

- Change from baseline in the CDR-SB at 24 months for subjects enriched by baseline PET SUVR, eg, between 1.2 and 1.6, in the combined studies
- Change from baseline in the ADCOMS at 24 months for subjects enriched by baseline PET SUVR, eg, between 1.2 and 1.6, in the combined studies
- The rate of change over time (mean slope) based on CDR-SB score over 24 months in the combined studies
- Time to worsening of CDR scores by 24 months (eg, the worsening of global CDR score is defined as an increase from baseline by at least 0.5 points on the global CDR scale on 2 consecutive scheduled visits at which global CDR is undertaken) in the combined studies
- Time to conversion to dementia by 24 months for subjects who were not clinically staged as dementia at Baseline based on clinical diagnosis in the combined studies (revised per Amendment 01)
- Change from baseline in CDR-SB at 27 months (ie, 24 months of treatment plus 3 months posttreatment follow-up) in the combined studies (revised per Amendment 01)
- Change from baseline in ADAS-cog14, MMSE, and FAQ at 24 months in the combined studies
- Change from baseline in ADAS-cog14 Word List (immediate recall and delayed recall) at 24 months in the combined studies (revised per Amendment 01)

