9.7.1.7.3 PHARMACODYNAMIC, PHARMACOGENOMIC, AND OTHER BIOMARKER ANALYSES

The analysis of the biomarker endpoints defined as below will be performed to compare elenbecestat versus placebo using the appropriate prespecified statistical methods including MMRM model, ANCOVA, or non-parametric methods if the data is not normally distributed, etc. These analyses will be conducted without adjustment for multiplicity or sequential testing. For each endpoint, the treatment effect for elenbecestat 50 mg per day versus placebo will be tested at a significance level of 2-sided alpha = 0.05. (revised per Amendment 05)

- Change from baseline in tau PET signal at 24 months (revised per Amendment 05)

- Change from baseline in CSF biomarkers t-tau and p-tau at 24 months
- Change from baseline in CSF amyloid biomarkers A β (1-42), and A β (1-x) at 24 months (revised per Amendment 04)
- Change from baseline in total hippocampal volume at 12 and 24 months using vMRI
- Change from baseline in fMRI parameters as appropriate (revised per Amendment 06)
- Change from baseline in plasma amyloid biomarker (eg, A β (1-x)) at all assessments (revised per Amendment 06)
- Change from baseline in potential plasma and CSF biomarkers of AD (eg, NFL, VILIP1, YKL-40, and Ng) (revised per Amendment 06)

The relationship between exposure (in CSF, plasma) of elenbecestat with potential biomarkers of Alzheimer's disease as deemed appropriate will be evaluated using appropriate statistical model with the continuous changes in biomarker at 24 months as response variables and exposure variables (in CSF, plasma) of elenbecestat as independent variables.

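### As worded, a non-significant primary stops the key secondary analyses from being performed, leaving the Core Study with no between-arm amyloid PET estimate and no full-FAS ADCOMS comparison

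*Protocol*

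**What the plan says.** Section 9.7.1.6.2 opens its key secondary part with "The key secondary analyses will be performed only if the primary analysis is significant". A separate sentence then sets up sequential testing at two-sided 0.05, under which "any test will start only if the test with higher hierarchical order is significant".

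Section 9.7.1.1.2 names the key secondary endpoints. They are "Change from baseline in ADCOMS at 24 months in the combined studies", then "Change from baseline in amyloid PET SUVR at 24 months for brain amyloid levels in the combined studies", then the same SUVR endpoint in the individual studies.

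The other secondary analyses in 9.7.1.6.2 carry no such condition. One of them reads "The change from baseline in CDR-SB and ADCOMS at 24 months will be analyzed using the same MMRM model as the primary analysis", restricted to subjects within a baseline PET SUVR range that is given only as an example (1.2 to 1.6).

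Section 9.7.1.7.3 lists the biomarker comparisons between arms and says "These analyses will be conducted without adjustment for multiplicity or sequential testing". The list covers tau PET, CSF tau and Aβ, plasma Aβ, hippocampal volume, fMRI and exploratory markers. Neither it nor the endpoint list in 9.7.1.1.3 contains amyloid PET.

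**The concern.** A fixed sequence needs only to restrict which results may be claimed as confirmatory. This text restricts which analyses are done. The restriction falls on the one Core Study comparison of brain amyloid by PET.

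Section 9.2.4 gives evaluating the drug's effect on brain amyloid at 12 and 24 months as one of the two main reasons for amyloid PET imaging, and substudy participants are scanned for that purpose. If CDR-SB is negative, a central question is whether plaque was reduced without clinical benefit or was not reduced. The plan as worded gives no PET estimate to answer it.

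The ADCOMS result is also the wrong way round. After a negative primary, a treatment comparison is planned in a selected subset but not in the full population from which it is drawn.

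**Working it through.** **Which comparisons survive a non-significant primary, read literally**

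| Comparison between arms | Where planned | Depends on primary? |
|---|---|---|
| ADCOMS, full FAS | 9.7.1.6.2, key secondary | Yes |
| Amyloid PET SUVR, pooled and within study | 9.7.1.6.2, key secondary | Yes |
| ADCOMS and CDR-SB, SUVR-enriched subset | 9.7.1.6.2, other secondary | No |
| ADAS-cog14, MMSE, FAQ, full FAS | 9.7.1.6.2, other secondary | No |
| CSF Aβ(1-42), CSF Aβ(1-x), plasma Aβ(1-x) | 9.7.1.7.3 | No |
| Tau PET, CSF tau, hippocampal volume, fMRI | 9.7.1.7.3 | No |

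Two further places mention amyloid PET or ADCOMS.

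- The ANCOVA at the end of 9.7.1.6.2 relates clinical change (including ADCOMS) to biomarker change (including amyloid PET), with treatment group as a factor. Amyloid PET is an explanatory variable there, so its difference between arms is not estimated. The treatment term for ADCOMS is adjusted for a post-randomization biomarker change, so it is not the FAS treatment effect.
- Appendix 5 plans delayed-start and MMRM analyses of amyloid PET SUVR in the Extension Phase. These come later, include only Core Study completers who enter the Extension, and belong to a phase that ends if a lack of positive benefit-risk is determined.

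**How often the condition fails**

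Inputs from 9.7.2: placebo mean change 1.46, SD 2.05, 25% reduction, 30% dropout, 950 per arm, two-sided alpha 0.05, 90% power.

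1. Difference: 0.25 × 1.46 = 0.365.
2. Evaluable n per arm: 2 × (1.960 + 1.282)² × 2.05² / 0.365² = 663. Dividing by 0.70 gives 948 per arm, 1896 in total. The protocol's 1900 is reproduced.
3. Evaluable per arm as planned: 950 × 0.70 = 665. SE = 2.05 × √(2/665) = 0.1124.
4. Power: 0.365 / 0.1124 = 3.247, and Φ(3.247 − 1.960) = 0.901 (0.900 with the noncentral t).
5. Probability that the key secondaries are not performed = 1 − [1 − Φ(1.960 − δ/SE) + Φ(−1.960 − δ/SE)], where δ is the true reduction × 1.46.

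| True reduction in CDR-SB change | Key secondaries not performed |
|---|---|
| 0% | 95.0% |
| 5% | 90.0% |
| 10% | 74.5% |
| 15% | 50.5% |
| 20% | 26.2% |
| 25% (design) | 9.9% |

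Only the 25% row is the protocol's assumption. The others are an assumed range.

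**The case against.** The strongest reply is that the opening sentence is ordinary language for a testing hierarchy. The next sentence speaks of tests, the ADCOMS and amyloid PET paragraphs describe their models without repeating the condition, and 9.7.1 promises within-study analyses to confirm trends unless otherwise specified. A statistical analysis plan, not shown here, could say how results are reported once the sequence stops. That reading is possible. But the two sentences do separate jobs: the second already protects alpha, and the first adds that the analyses themselves depend on the primary. This is a rule the protocol states, not a detail it leaves open. If only confirmatory testing was meant, the rewording below simply says so.

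Several stronger readings are tempting but not supported.

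- **That a failed trial could say nothing about amyloid.** CSF and plasma Aβ are compared between arms whatever the primary shows (for example "Change from baseline in CSF amyloid biomarkers"), and 9.2.4 treats Aβ(1-x) as the best measure of total pharmacologic effect. Only the PET measure is lost. Soluble Aβ shows target engagement, not change in plaque.
- **That selective reporting is built into the plan.** ADCOMS is a weighted sum of CDR, MMSE and ADAS-cog items, and CDR-SB, ADAS-cog14 and MMSE are all analysed on the full FAS. The text shows an awkward consequence, not an intention. Those scales still do not give the ADCOMS estimate.
- **That 9.2.1 is contradicted.** It says "it is proposed that several biomarkers will be utilized during this study without a specific hierarchical approach", but this can be read as covering only the endpoints in 9.7.1.1.3, and those are indeed tested without a hierarchy.
- **That amyloid PET is also dropped whenever ADCOMS fails.** The order is inferred from the listing in 9.7.1.1.2, and the rule within the sequence concerns tests starting, not analyses being performed.

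It is also fair to say that 10% and 95% are just the design's type II error and one minus alpha. They show how often the rule applies, not how much harm it does.

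**Conclusion.** The point holds in limited form. Followed as written, a non-significant CDR-SB result leaves the Core Study with no between-arm estimate of brain amyloid by PET and no full-FAS treatment comparison of ADCOMS, while ADCOMS in the SUVR-enriched subset is still analysed. This happens with probability about 10% at the design effect and 95% under no effect, given the sample-size assumptions in 9.7.2 and a literal reading of the opening sentence. The sequential procedure is sound, and the primary inference, type I error and data collection are unaffected. The data would exist either way; what is missing is a planned analysis of them in the case where it is most needed.

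**What to change.** Reword the opening of the key secondary part of 9.7.1.6.2, for example:

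> Key secondary endpoints will be tested confirmatorily in sequence only if the primary analysis is significant. All key secondary analyses will be performed and reported with LS mean difference, 95% CI and nominal p-value whatever the outcome, and labelled descriptive once the sequence has stopped.

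As a minor tidy-up, state in 9.2.1 that the remark about having no hierarchy refers to the biomarker endpoints other than amyloid PET.

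The cost is one sentence and one clarification. No alpha is spent, and no subjects, scans or visits are added. The only obligation is to label nominal results as descriptive.

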- n: Amyloid PET scanning will be performed with a locally approved amyloid imaging agent (eg, Neuraceq, if available or an agent under clinical investigation if no agents are approved locally); for subjects participating in the amyloid PET substudy, the imaging agent must remain unchanged throughout the study. Subjects who are assessed by both amyloid PET and CSF are required to wait for a minimum of 48 hours between the 2 procedures (revised per Amendment 02). A positive amyloid result is needed for only 1 of the 2 amyloid eligibility procedures to confirm eligibility (ie, even if 1 of the 2 results is negative for amyloid, the subject would still be eligible under the other positive result). For subjects who are approved for rescreening, the amyloid PET need not be repeated for eligibility if confirmed amyloid positive during the original screening procedure. If a rescreened subject will participate in the longitudinal amyloid PET substudy, quantitative PET collection should be repeated if the original PET collection was done greater than 90 days from the date of the original screening procedure. (revised per Amendments 05 and 06)
- o: For those subjects who consent to the longitudinal CSF substudy, CSF should be collected at the same time of day for each assessment, preferably fasting or at least 2 hours post meal. For those subjects who consent to CSF and amyloid PET eligibility assessments, the 2 assessments should be separated by at least 48 hours between the 2 procedures. For these subjects, a positive amyloid result is needed for only 1 of the procedures to confirm eligibility (ie, even if 1 of the 2 results is negative for amyloid, the subject would still be eligible under the other, positive result). For subjects who are approved for rescreening, the CSF need not be repeated for eligibility if confirmed amyloid positive during the original screening procedure. A gravity drip collection method must be used. Subjects will be encouraged to stay at the site after completion of LP for medical observation. (revised per Amendments 05 and 06)
- p: Subjects receiving concomitant anticoagulation/antiplatelet therapy should have prothrombin time and INR (derived from prothrombin time) before LP; if they are assessed by the investigator to be at risk for bleeding, they are to be excluded from CSF collection. (revised per Amendments 01 and 02)

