Table 5 Schedule of Procedures/Assessments in Study E2609-G000-301 (Revised per Amendments 05 and 06)

Phase Period	Randomization														ED ^b	Follow-Up		UNS Visit ^d
	Treatment												14 ^c	15 ^c				
Visit ^a	2	3	4	5	6	7	8	9	10	11	12	13						
Day	1	15	29	57	85	183	274	365	456	547	638	729		757	813			
Week	1	3	5	9	13	27	40	53	66	79	92	105		109	117			
Weeks elapsed since 1st dose	0	2	4	8	12	26	39	52	65	78	91	104		108	116			
Nominal months elapsed since 1st dose	0		1	2	3	6	9	12	15	18	21	24		25	27			
Procedures/ Assessments																		

should be conducted within the 7 days before Visits 9 and 13. In the event of an Unscheduled Visit, the investigator in consultation with the medical monitor will determine whether or not a safety MRI should be conducted. If an ED Visit takes place, an MRI is to be conducted if not already performed during the preceding 90 days.

- t: Amyloid PET scanning (if subject has consented to optional substudy) will be performed with a locally approved amyloid β imaging agent (eg, Neuraceq, if available) or an agent under clinical investigation if no agents are approved locally; the imaging agent must remain unchanged for an individual subject throughout the study. An amyloid PET scan will only be performed at an ED Visit if the subject has been treated with study drug for at least 39 weeks and at least 6 months has elapsed since the prior amyloid PET scan was performed. (revised per Amendments 04 and 05)
- u: For subjects who consent to the tau PET longitudinal substudy, tau PET will be conducted at 24 months of treatment during the Core Study (or at the ED Visit, provided the subject has received at least 39 weeks of study drug). At the 24 month timepoint (or at the ED Visit), the amyloid and tau PET scans can be performed in either order but must be at least 48 hours apart. If the subject has also consented to the longitudinal CSF substudy, the longitudinal substudy assessments can be performed in any order, with at least 48 hours between each procedure. Tau PET scanning will be performed using a sponsor-supplied tau PET imaging agent, eg PI-2620. (revised per Amendment 05)

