9.7.1.6.1 PRIMARY EFFICACY ANALYSIS

The primary analysis will be based on an intent to treat philosophy without regard to adherence to treatment. The primary analysis of the change from baseline in CDR-SB at 24 months will be performed to compare elenbecestat 50 mg per day versus placebo using a linear mixed effects model for repeated measures (MMRM) on the FAS. The MMRM model will include fixed effects of treatment group, visit, treatment group by visit interaction, baseline CDR-SB, baseline CDR-SB by visit interaction, and randomization stratification variables (ie, region [7 levels], clinical dementia [yes, no], and concurrent AD medication use at randomization [Visit 2] [yes, no]). *ApoE4* status may be included in the model if appropriate. (revised per Amendments 01, 02, and 06) An unstructured covariance matrix will be employed to model the covariance of within subject effect; if MMRM fails to converge then a covariance structure with fewer parameters from the following list will be employed according to the prespecified order in the list until the MMRM converges. The list of covariance structure will include Heterogeneous Toeplitz, Toeplitz, Heterogeneous Compound Symmetry, and Compound Symmetry. This primary analysis will include all observed post baseline data of the change from baseline in CDR-SB without imputation of missing values. The treatment effect for elenbecestat versus placebo will be compared at 24 months based on MMRM model. The LS means and difference in LS means between elenbecestat treatment group and placebo, and corresponding 95% CI will be presented.

The null hypothesis is that there is no difference in the mean change from baseline in CDR-SB at 24 months between elenbecestat 50 mg per day and placebo. The corresponding alternative hypothesis is that there is a difference in the mean change from baseline in CDR-SB at 24 months between elenbecestat 50 mg per day and placebo.

The primary analysis will be repeated to minimize the impact of change in concomitant AD medications where efficacy data after initiation of new AD medications and increase of current AD medications will be censored.

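### The key secondary amyloid PET analysis pools SUVR over locally chosen tracers with no tracer term or common scale, so the estimated difference mixes units, although the test of no effect stays valid

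*Protocol*

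**What the plan says.** **Tracer.** Footnote n to Table 4 (Section 9.5.2.1) reads: "Amyloid PET scanning will be performed with a locally approved amyloid imaging agent (eg, Neuraceq, if available or an agent under clinical investigation", the investigational option applying where no agent is approved locally. Footnote t to Table 5 repeats the local choice and adds that "the imaging agent must remain unchanged for an individual subject throughout the study". Nothing in the text reviewed requires one tracer across subjects, sites or regions.

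**Endpoint.** Section 9.7.1.1.2 lists as a key secondary endpoint "Change from baseline in amyloid PET SUVR at 24 months for brain amyloid levels in the combined studies", and a further key secondary endpoint is the same change in the individual studies. The remaining one is ADCOMS.

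**Model.** Section 9.7.1.6.2 states: "The change from baseline in amyloid PET SUVR at 24 months will be analyzed using the same MMRM model as the primary efficacy analysis". It thus takes over the MMRM of Section 9.7.1.6.1 and replaces baseline CDR-SB by baseline SUVR. The terms are treatment, visit, treatment by visit, baseline, baseline by visit, and "randomization stratification variables (ie, region [7 levels], clinical dementia [yes, no], and concurrent AD medication use at randomization [Visit 2] [yes, no", with ApoE4 optional.

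**Enrichment.** CDR-SB and ADCOMS are also analysed, as other secondary endpoints, "for subjects enriched by baseline PET SUVR, eg, between 1.2 and 1.6, in the combined studies". The analysis section words it as "for subjects enriched by baseline PET SUVR between e.g. 1.2 and 1.6 on the FAS".

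Section 9.5.1.4.2 mentions a central PET reading group and a PET imaging manual, but says nothing about putting tracers on one scale.

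**The concern.** Requiring a fixed tracer within a subject concedes that tracers are not interchangeable. That rule protects each subject's own change score, but it does not make change scores comparable between subjects on different tracers. If two tracers have different dynamic ranges, the same SUVR change stands for different amounts of amyloid.

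The model being reused was written for CDR-SB, which has one scale for everyone. Applied to SUVR from several tracers, it imposes one line of change on baseline and one residual variance, and it reports a treatment difference that averages unlike units. Such a difference cannot be read as an amount of amyloid, and it would shift if more subjects were enrolled where another tracer is approved.

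SUVR supplies two of the three key secondary endpoints in the sequential testing procedure. The same section also uses change in amyloid PET as a predictor in the ANCOVA relating biomarker to clinical change. A single absolute SUVR range for enrichment would raise a related problem, since membership would depend partly on which agent a country had approved.

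**Working it through.** **Design figure.** The protocol gives no sample size, SD or power for SUVR. Its only design figure is for CDR-SB: with a difference of 0.25 × 1.46 = 0.365, SD 2.05, two-sided 5% and 90% power, 663 evaluable per arm are needed. Then 663/0.70 gives 948 per arm, 1,896 in total, against the stated 1,900. That figure reproduces, but it has no bearing on this point.

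**Assumptions.** The protocol states no tracer mix, SUVR variability or scale ratio, so everything below is illustrative. Tracer B reads (SUVR − 1) as k times tracer A. Baseline on the A scale is N(1.4, 0.2). There are 150 subjects per arm and the effect on the A scale is 0.03.

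**1. The estimate depends on the mix.** With a share q on tracer B, the expected pooled difference is 0.03 × (1 − q + qk). For k = 2 this is 0.030, 0.045 and 0.060 at q = 0, 0.5 and 1. For k = 1.25 and q = 0.5 it is 0.034. The underlying amyloid effect is identical in every case.

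**2. The baseline line.** If change on A is a + b(SUVR − 1), change on B is ka + b(SUVR − 1). Under a pure ratio the slope agrees and the intercept does not. If the tracers also differ in noise relative to spread, the slopes differ too. The stated model allows for neither, beyond what region happens to absorb.

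**3. Precision.** With a 50/50 mix the average effect is multiplied by (1 + k)/2 and the average variance by (1 + k²)/2, so relative efficiency is (1 + k)²/[2(1 + k²)]. With SD 0.09, z = 0.03/(0.09 × √(2/150)) = 2.887, and power is Φ(2.887 − 1.96) = 82.3%. Multiplying z by the square root of the efficiency gives:

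| k | efficiency | power | loss (points) |
|---|---|---|---|
| 1.25 | 0.988 | 81.8% | 0.5 |
| 1.5 | 0.962 | 80.8% | 1.5 |
| 2 | 0.900 | 78.2% | 4.1 |

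A simulation of 2,000 runs with the same SD gave pooled against common-scale power of 82.2% vs 82.2%, 81.6% vs 83.2% and 77.3% vs 81.2%. The common-scale figure should not depend on k, so its movement between 81.2% and 83.2% shows the simulation noise.

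**4. Validity.** A second simulation (SD 0.08, ANCOVA on baseline without region or visit terms, 3,000 runs) gave type I error for pooled SUVR of 4.6%, 4.5%, 5.3% and 4.8% at k = 0.6, 1, 1.5 and 2. Pooled against common-scale power was 88.3% vs 89.9%, 90.0% vs 90.0%, 88.4% vs 89.7% and 85.5% vs 89.7%. The largest loss is 4.2 points.

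**5. Enrichment range.** Read on tracer B, 1.2 to 1.6 corresponds on the A scale to 1 + 0.2/k up to 1 + 0.6/k. The share inside is Φ((upper − 1.4)/0.2) − Φ((lower − 1.4)/0.2):

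| k | A-scale range | share inside |
|---|---|---|
| 1 (tracer A) | 1.20–1.60 | 68% |
| 1.25 | 1.16–1.48 | 54% |
| 1.5 | 1.13–1.40 | 41% |
| 2 | 1.10–1.30 | 24% |

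If tracer B reads lower instead, the range moves the other way: 1.25–1.75 (73%) at k = 0.8 and 1.33–2.00 (63%) at k = 0.6.

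**The case against.** The strongest reply is that inference is not damaged. Each subject's change is on one scale, randomisation is stratified by region, and region is in the model and partly stands in for local tracer approval. PET is tested only after CDR-SB succeeds. A reader might infer from the mixed units that the PET tests are invalid. The protocol does not support that, and the simulated type I error stays near 5%. Treatment also remains randomised within any baseline SUVR range, so a mixed range blurs who is selected without biasing the comparison.

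A reader might also infer that one range is fixed for every tracer. It is not: both places mark 1.2 to 1.6 as an example, so the final range is open. Nor does the protocol say that SUVR is unstandardised. Reference region and any cross-tracer adjustment are unstated, and the imaging manual or a SAP, neither of which was available for this review, might supply them. The protocol text reviewed is also incomplete.

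Finally, every quantity in the illustration is assumed. The rule of one tracer per subject shows that tracers are not treated as interchangeable, but it does not show by how much they differ.

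All of this limits the size of the point. What remains is that the protocol does not leave the SUVR model open. It prescribes one by reference to a fully listed model that takes no account of tracer, while allowing tracers to differ. Region as a main effect shifts the mean, but it does not put treatment effects, intercepts or residual variances on one scale, and a region can contain countries with different approved agents.

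**Conclusion.** The point holds as one about the meaning and precision of the estimate. For two of the three key secondary endpoints, the prescribed model would give an LS-mean difference in mixed SUVR units that depends on the tracer mix. If only one tracer is used in practice, the problem disappears.

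The precision cost is small: about 0.5 points of power at an assumed scale ratio of 1.25, rising to about 4 points at a ratio of 2, with two tracers used equally. The effect on the reported difference can be larger; at a ratio of 2 it runs from 0.030 to 0.060 for the same underlying effect, depending only on the mix.

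For enrichment the point is conditional. If the example range were adopted as one absolute range, it would select different amyloid burdens by tracer: 68% of subjects on one tracer against 54% to 24% on the other, for assumed ratios of 1.25 to 2. It should be corrected, but it does not threaten the validity of the trial's tests.

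**What to change.** In Section 9.7.1.6.2, replace the plain reuse of the CDR-SB model for PET by one of two routes:

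- **Preferred:** convert each scan to a common scale (for example Centiloid) before pooling, and use change and baseline on that scale in the MMRM and in the ANCOVA relating biomarker to clinical change.
- **Otherwise:** keep SUVR and add tracer, tracer-by-visit and baseline-SUVR-by-tracer terms. These repair the fit but not the units, so the treatment difference should also be reported by tracer.

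In Sections 9.7.1.1.2 and 9.7.1.6.2, replace the example enrichment range by one set on the common scale, or by tracer-specific ranges, fixed before unblinding.

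The cost is protocol or SAP wording and a conversion step by the central PET laboratory on scans already collected; no new scans or visits are needed. The drawback is that a tracer without a validated conversion has to take the tracer-adjusted SUVR route.
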